5.0 Selection of patients

5.1 Pre-randomisation evaluation

All patients presenting at the ED, at each participating hospital, will be first assessed by the treating ED clinical team and receive standard care in accordance with the current best practice. The treating ED clinical team will then contact the dedicated ProMISe Research Nurse for their hospital.

Standard care should include the following assessments or procedures that are required to evaluate the suitability of patients for the trial:

- in patients with suspected or confirmed infection this should include having arterial or venous blood lactate measurement to assess for the presence of hypoperfusion;
- a first dose of intravenous (IV) antimicrobial therapy commenced prior to randomisation.

Additional investigations and evaluation of the suspected infection will occur as part of standard clinical management.

It is also expected that a minimum IV fluid challenge of one litre fixed bolus within sixty minutes, will be given as part of standard resuscitation for patients with suspected or confirmed infection and evidence of hypotension.

5.2 ProMISe Screening Log

The ProMISe Screening Log will be supplied by the ICNARC CTU and maintained by the site in the Investigator Site File. This should record each patient who meets all the inclusion criteria but was not randomised and each patient who meets all the inclusion criteria and one of more of the exclusion criteria. Details of why the patient was not randomised should be recorded. The ProMISe Screening Log should be sent to the ICNARC CTU, when requested, with patient identifiers removed prior to sending.

5.3 Delivery at site

Whereas the content of the early, goal-directed, resuscitation protocol to be evaluated will be identical across all sites, delivery of the protocol will be locally determined (i.e. pragmatic) and implementation will be delegated to the local investigators to suit their local NHS setting. Delivery of the protocol includes the ability to transition from the ED to another location within the hospital, during the six-hour protocol time frame, where clinically indicated.

5.4 Patient eligibility

Once a potential patient is identified, it is imperative that the following four criteria are satisfied, as soon as possible, and in any order following presentation at the ED, within a maximum of six hours.

5.4.1 Inclusion criteria

- 1) Refractory hypotension or hypoperfusion
 - a. Refractory hypotension is confirmed by the presence of a systolic blood pressure of less than 90 mmHg or a mean arterial pressure of less than 65 mmHg, despite a minimum IV fluid challenge of one litre fixed bolus within sixty minutes (including IV fluids administered by pre-hospital personnel)

or

- b. Hypoperfusion is confirmed by a blood lactate concentration of 4mmol l⁻¹ or greater
- 2) Known or presumed infection
- 3) Two or more Systemic Inflammatory Response Syndrome (SIRS) criteria:
 - a) core temperature of 36°C or less or of 38°C or more;
 - b) heart rate of 90 beats min⁻¹ or more;
 - c) respiratory rate of 20 breaths min⁻¹ or more(or hyperventilation indicated by either a PaCO₂ less than 4.3 kPa or mechanical ventilation for an acute process); or
 - d) white blood cell count of $4x10^9 \, l^{-1}$ or less or of $12 \times 10^9 \, l^{-1}$ or greater (or the presence of greater than 10% immature neutrophils (bands)).
- 4) First dose of IV antimicrobial therapy initiated prior to randomisation.

Eligibility needs to be confirmed as soon as possible. Each inclusion criterion needs to be met once over a maximum time period of six hours. After this time, resuscitation is no longer considered to be early and the patient is not eligible for entry into ProMISe.

5.4.2 Exclusion criteria

- 1) Age less than 18 years
- 2) Known pregnancy
- 3) Primary diagnosis of:
- an acute cerebral vascular event
- acute coronary syndrome
- acute pulmonary oedema
- status asthmaticus
- major cardiac arrhythmia (as part of primary diagnosis)
- seizure
- drug overdose
- injury from burn or trauma
- 4) Haemodynamic instability due to active gastrointestinal haemorrhage
- 5) Requirement for immediate surgery
- 6) Known history of AIDS
- 7) Do-Not-Attempt-Resuscitation (DNAR) status
- 8) Advanced directives restricting implementation of the resuscitation protocol
- 9) Contraindication to central venous catheterization
- 10) Contraindication to blood transfusion
- 11) Attending clinician deems aggressive resuscitation unsuitable
- 12) Transferred from another in-hospital setting
- 13) Not able to commence resuscitation protocol within one hour of randomisation or complete six hours of protocol treatment from commencement
- N.B. If during screening, a patient is found to be participating in another interventional study/trial, then please contact the ICNARC CTU on [name] to discuss their participation in ProMISe.

6.0 Randomisation procedures

The approaching, consenting and randomisation procedures must be completed within two hours of confirmation of eligibility.

6.1 Randomisation and allocation

A dedicated, 24 hours/seven days per week, telephone randomisation service will be available. In addition, during recruitment, the ProMISe Clinical Advisor, or one of the clinical co-investigators, will be available 24 hours/seven days per week to address any emergency recruitment/randomisation issues.

Randomisation [contact]
Emergency 24/7 [contact]

Allocation to one of the two arms will be by randomised permuted blocks (with variable block lengths of 4, 6 and 8), stratified by recruiting site. As this is a large, multi-centre trial, the risk of chance imbalance in prognostic factors is low and the need to randomise patients during a very short time-window mandates that the randomisation process be as simple as possible. For these reasons, we have elected not to stratify the randomisation process on additional prognostic factors.

Patient randomisation must be performed prior to commencement of any trial intervention.

Following pre-randomisation evaluations (as detailed in Section 5.1), confirmation of eligibility and consent of a patient at a site, the ProMISe Randomisation - Eligibility Form must be fully completed prior to telephoning the randomisation service. The eligibility criteria will be reviewed during the randomisation telephone call. A ProMISe Trial Number and treatment allocation will be assigned, and time of randomisation and date/time of T1 (end of the 'golden' hour) will be stated at the end of the call. These must be recorded at the site by the caller on the ProMISe Randomisation – Eligibility Form.

The telephone randomisation service is provided by Sealed Envelope (http://www.sealedenvelope.com/)

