1.0 Protocol summary

1.1 Summary of trial design

Title:	A multicentre, randomised controlled trial of the clinical and
Title.	cost-effectiveness of early, goal-directed, protocolised resuscitation for
	emerging septic shock
Short Title/acronym:	Protocolised Management In Sepsis/ProMISe
REC number:	10/H0722/42
Sponsor name and reference:	ICNARC and ICNARC/01/01/09
Funder name and reference:	NIHR HTA Programme and 07/37/47
ISRCTN number:	36307479
NIHR CRN Portfolio ID number:	9820
CSP reference:	39113
	An open, prospective, multicentre randomised controlled trial
Design: Overall aim:	To evaluate a resuscitation protocol, with pre-determined
	haemodynamic goals, compared with usual resuscitation
Primary endpoints:	90-day all cause mortality
	Incremental cost per QALY gained at one year
Secondary endpoints:	To compare:
	mortality at one year;
	health-related quality of life at 90 days and one year; resource use at 90 days and one year;
	requirement for and duration of critical care organ support;
	length of stay in the Emergency Department, critical care unit and acute
	hospital.
	To estimate :
	lifetime incremental cost-effectiveness.
Target accrual:	1260
Inclusion criteria:	Following presentation at the Emergency Department, the four criteria
	to be met, once, in any order, over a maximum of six hours:
	refractory hypotension or hypoperfusion
	known or presumed infection
	two, or more, systemic inflammatory response syndrome
	(SIRS) criteria
Fredrick mittage	first dose of IV antimicrobial therapy initiated Age less than 18 years
Exclusion criteria:	Known pregnancy
	Primary diagnosis of an acute cerebral vascular event, acute coronary
	syndrome, acute pulmonary oedema, status asthmaticus, major cardiac
	arrhythmia (as part of primary diagnosis), seizure, drug overdose, injury
	from burn or trauma
	Haemodynamic instability due to active gastrointestinal haemorrhage
	Requirement for immediate surgery
	Known history of AIDS
	Do-Not-Attempt-Resuscitation (DNAR) status
	Advanced directives restricting implementation of the protocol Contraindication to central venous catheterization
	Contraindication to blood transfusion
	Attending physician deems aggressive care unsuitable
	Transferred from another in-hospital setting
	Not able to commence protocol within one hour of randomisation or
	complete six hours of protocol treatment from commencement
Planned number of sites:	Minimum 48

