3.2.3 Site activation

Once the ICNARC CTU have confirmed that all documentation is in place, a site activation email will be issued to the PI, at which point, the site may start to screen for eligible patients.

Once the site has been activated, the PI is responsible for ensuring:

- adherence to the most recent version of the protocol;
- all relevant site staff are trained in the protocol requirements;
- all trial staff are trained appropriately, including GCP trained;
- appropriate recruitment and care for patients in the trial;
- timely data entry; and
- prompt notification of all adverse events (as specified in Section 11).

The PIs, other investigators and all local staff involved in the conduct of the trial at the site must be identified on the ProMISe Site Research Staff Contact Form and ProMISe Delegation of Trial Duties Log, held at site, and copied to the ICNARC CTU when any changes are made, to be authorised.

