6.2.2 Trial equipment

Trial equipment will be stored on a ProMISe trolley. When a patient is randomised to receive the early, goal-directed, protocolised resuscitation, this trolley will be used.

The equipment will include:

- PreSep[™] ScvO₂ catheter;
- Edwards Vigileo monitor;
- early, goal-directed, resuscitation protocol.

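### In an open trial stratified only by site, short permuted blocks whose lengths are printed in the site-held protocol weaken allocation concealment; the effect is modest and cheap to reduce

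*Protocol*

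**What the plan says.** Section 6.1 reads: "Allocation to one of the two arms will be by randomised permuted blocks (with variable block lengths of 4, 6 and 8), stratified by recruiting" hospital. No other stratification factor is used. Section 1.1 describes the design as "An open, prospective, multicentre randomised controlled trial".

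Each allocation is known at the site. Of the trial number, allocation and times given on the call, section 6.1 says: "These must be recorded at the site by the caller on the ProMISe Randomisation – Eligibility Form". Section 6.2.2 adds: "When a patient is randomised to receive the early, goal-directed, protocolised resuscitation, this trolley will be used". Section 9.1 keeps the original paper CRFs at the site.

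Sites hold and use the protocol. Section 3.2.3 makes the principal investigator responsible for "adherence to the most recent version of the protocol" and for ensuring that "all relevant site staff are trained in the protocol requirements". Nothing in the document restricts the block lengths to people outside the sites.

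Two exclusions in section 5.4.2 rest on judgement made before the call. Number 11 is "Attending clinician deems aggressive resuscitation unsuitable". Number 13 is a forecast of whether the protocol can be started in time and delivered for its full six hours.

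The protocol also contains safeguards:
- allocation by a central telephone service, with varying block lengths (6.1);
- an eligibility form completed before the call, and criteria reviewed during it (6.1);
- a screening log with reasons for patients who met the inclusion criteria but were not randomised (3.2.1 and 5.2);
- a supporting analysis adjusted for covariates chosen in advance (15.2).

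**The concern.** A central telephone service hides the list, but concealment also requires that the next entry cannot be inferred from earlier ones. Three features combine against that here. The trial is open, the only stratum is the site (so the site's own history is the complete sequence), and the blocks are short. Printing the lengths tells the reader how far an imbalance can run before it must reverse.

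Anyone who can guess better than chance, and who can influence whether a borderline patient is judged suitable, could let expected allocation affect entry. The arms would then differ in baseline risk. The primary comparison of 90-day mortality is an unadjusted Fisher's exact test (15.2), which would carry that difference through. The co-primary cost per QALY would carry it too.

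**Working it through.** **Inputs.** Target 1260 patients (15.7) and 48 sites (3.1 and 15.7): 1260/48 = 26.25, so about 26 per site. Block lengths 4, 6 and 8 by site (6.1). Assumption: the three lengths are equally likely, because the protocol gives no weights. The protocol states no predictability figure to reproduce. Its sample size does reproduce: 40% against 32%, 80% power and two-sided 5% give 589 per arm with continuity correction. Nothing below affects it.

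**Exact start of a sequence.** The probability of opening with two in a given arm is 1/6, 1/5 and 3/14 for lengths 4, 6 and 8. The chance that the other arm follows is 1, 3/4 and 4/6 respectively.
- After two alike: (1/6 × 1 + 1/5 × 3/4 + 3/14 × 4/6) / (1/6 + 1/5 + 3/14) = 0.4595/0.5810 = 0.79.
- After three alike, only 6 and 8 remain, with weights 0.0500 and 0.0714: (0.0500 × 1 + 0.0714 × 4/5)/0.1214 = 0.88.
- After four alike: certain. This needs a first block of 8 that opens with four alike, probability (1/3) × (2/70), about 1% of sequences.

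**Whole sequence.** Simulated sites of 26 patients, with two guessers who have the full site history. One knows the lengths and updates exactly; the other simply guesses the arm that is behind.

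| Quantity | Lengths 4, 6, 8 | Lengths 8 to 16 |
|---|---|---|
| Correct, lengths known | 67% | 63% |
| Correct, tally only | 67% | 63% |
| Callable at 75% or more, lengths known | 36% | 13% |
| Certain, lengths known | 2.2% to 2.5% | about 0.5% |
| SD of arm difference, one site | 1.1 | 1.5 |
| SD of arm difference, 48 sites | about 7 | about 10 |

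The range for certain calls is the spread between simulation runs. About one site in five meets at least one certain call under 4, 6 and 8. Other weights for those lengths move the 67% to between 66% and 69%.

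**Tally alone.** The arms are unequal before 63% of allocations. The guess is then right 75% of the time when one arm leads by one, 85% by two and 93% by three.

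**Partial view.** A person who sees each past allocation with probability one half is right 55% of the time; with probability one third, 54%.

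**Illustration of bias.** Let a be guess accuracy and Δ the mortality difference between patients entered under opposite guesses. Bias = (2a − 1)Δ. Δ has no source in the protocol; 2 to 5 points is an assumption.
- a = 0.67: multiplier 0.34, bias 0.7 to 1.7 points against the 8-point target.
- a = 0.63: multiplier 0.26, bias 0.5 to 1.3 points.
- Reduction: (0.34 − 0.26)/0.34, about a quarter.

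With SE = √(2 × 0.4 × 0.6/630) = 0.0276, a bias of 0.7 points gives a two-sided type I error of about 5.7%, and 1.4 points about 7.9%.

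**The case against.** The strongest reply is that the printed lengths are not the main cause. A plain tally guesses as well as full knowledge of the lengths, so deleting them alone leaves accuracy at 67%. That stands, and it is why the fix must also lengthen the blocks.

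Second, 67% is an upper case. It needs one person with the whole site history. Exclusion 11 belongs to the attending clinician, section 16.5 describes frequent rotation and multiple shifts among ED staff, and research nurse time is 0.33 full-time equivalent per hospital (3.1) against a 24-hour service. This also stands for most ED staff. It does not cover the research nurse, whom the ED team contacts before randomisation (5.1), or the principal investigator. Section 16.5 offers rotation as a protection against contamination, not against prediction.

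Third, the form completed before the call, the review on the call and the screening log constrain selection and leave a trace. They do so only in part: a patient judged unsuitable generates no call, and the log would show exclusion 11 as a valid reason.

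A reader might infer that sites can routinely foresee allocations because the lengths are printed, that the person who can guess is the one who decides entry, or that the mortality comparison is biased by one to two points. The documents support none of these. Certainty is rare, no section says the holder of the tally applies exclusion 11, nothing shows that selection took place, and the bias range rests wholly on an assumed Δ.

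**Conclusion.** The point holds in limited form. Short blocks within site in an open trial make allocation guessable above chance for someone with the full site tally: about 67% correct. If that person also uses the printed lengths, 36% of allocations can be called with at least 75% probability. Disclosure itself adds certain calls for about 2% of allocations. Staff with a partial view gain little. The safeguards reduce the opportunity to act on a guess through exclusions 11 and 13 without removing it. The direction and size of any resulting bias are unknown.

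The percentages rest on 26 patients per site, equally likely lengths and a complete history. This is a worthwhile, inexpensive tightening of concealment, not an error that undermines the trial or its sample size.

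**What to change.** In section 6.1, replace the stated lengths with wording such as: *permuted blocks of varying length, stratified by site; lengths held by the randomisation service and trial statistician and not disclosed to sites*. Because 4, 6 and 8 are already in circulation, ask the randomisation service to generate all remaining blocks from a different, longer and undisclosed mix, for example 8 to 16. Give the lengths in the final report.

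The cost is a wording amendment and new lists from the existing service. Balance loosens slightly: the SD of the arm difference rises from about 1.1 to 1.5 patients at a 26-patient site, and from about 7 to 10 patients over 48 sites, which is negligible for power with 1260 patients.

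The gain is modest. Even a guesser who learned the new lengths would fall only from 67% to about 63% correct, though calls at 75% or more drop from 36% to about 13%. It applies only to patients not yet randomised. This is version 2.3, dated 31/08/2012, and the document does not say how many patients remain.

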6.2 Trial materials

6.2.1 Central venous oxygenation catheter and monitor

Continuous $ScvO_2$ measurement will be undertaken via the $PreSep^{TM}$ central venous oximetry catheter. The $PreSep^{TM}$ catheter is manufactured by Edwards Lifesciences Limited and is commercially available, and licensed for this purpose, in the UK. The catheter is a 20cm 8.5 French triple lumen central venous catheter (CVC), and has two 18-gauge lumens and a single 15-gauge lumen. In addition, the $PreSep^{TM}$ has a fibreoptic bundle used for oximetric $ScvO_2$ monitoring. When the fibreoptic port is connected to a calibrated Edwards Vigilance or Vigileo monitor, the catheter is capable of providing a continuous $ScvO_2$ reading. The catheters and monitor will be supplied to sites for ProMISe and used only for those patients randomised to receive the early, goal-directed, resuscitation protocol.

The monitor is provided on loan free-of-charge to all sites participating in the trial for the duration of the trial period.

There is a 24 hours/seven days per week support to address any emergency technical issues with the trial equipment.

Edwards Lifesciences support [contact]

6.2.2 Trial equipment

Trial equipment will be stored on a ProMISe trolley. When a patient is randomised to receive the early, goal-directed, protocolised resuscitation, this trolley will be used.

The equipment will include:

- PreSep[™] ScvO₂ catheter;
- Edwards Vigileo monitor;
- early, goal-directed, resuscitation protocol.

6.3 Modification of early, goal-directed, protocolised resuscitation

Patients will be continuously monitored during the six hours of the delivery of early, goal-directed, protocolised resuscitation. At any time during the six-hour resuscitation period and, if clinically indicated, individual elements of the early, goal-directed, resuscitation protocol can be modified or discontinued at the clinical discretion of the treating clinician(s) for patient safety. For example, the protocol may be modified due to the development of: acute pulmonary oedema; an arrhythmia resulting in cardiovascular instability; or a blood transfusion reaction.

Ultimate responsibility for the safe and effective implementation of the early, goal-directed, protocolised resuscitation remains with the participating trial site.

Patients who do not receive any or all of the elements of the early, goal-directed, protocolised resuscitation will be followed up, according to the trial follow-up schedule, and analysed according to the intention-to-treat principle.

7.0 Trial treatment

7.1 Summary

It is necessary that patients are randomised, as soon as possible, and within two hours of meeting the eligibility criteria.

Eligible patients will be randomised to receive either:

six hours of early, goal-directed, protocolised resuscitation;

or

• usual resuscitation (standard UK resuscitation practice).

For patients randomised to early, goal-directed, protocolised resuscitation, the clinical protocol will be commenced immediately following randomisation and within "one hour" ("one hour" to be defined as up to the end of the following hour i.e. if the patient is randomised at 9:24 am they have to start early, goal-directed, protocolised resuscitation by 11:00 am). Simple protocol guides will be provided. Patients randomised to usual resuscitation will continue as usual.

7.1.1 Early, goal-directed, protocolised resuscitation

If not already initiated, supplemental oxygen is to be administered, with intubation and mechanical ventilation as needed, to achieve a pulse oximeter reading of 93% or greater. The following elements of the resuscitation protocol may be administered in series or simultaneously, depending on the clinical assessment of the patient's requirements. For example, if a patient is in extremis, the clinical team may decide to administer IV fluids in conjunction with vasopressors. Each element of the protocol should be initiated, if there are no potential condraindication(s), and should be delivered at the discretion of the treating clinician(s) dependent upon patient requirements.

Line insertion

Line insertion involves both the $PreSep^{TM}$, a CVC with continuous oximetric monitoring capability, inserted either into the subclavian or internal jugular vein, and an arterial line. The CVC with continuous oximetric monitoring capability is inserted using standard techniques for central access and calibrated to achieve a $ScvO_2$ reading. All CVCs will be inserted and managed according to the guidelines of the CVC Care Bundle (*NHS Saving Lives High Impact Intervention: Number 1*¹⁷).

Fluid resuscitation

Fluid boluses in half-litre, or equivalent increments, are given every thirty minutes until a minimum central venous pressure (CVP) of 8 mmHg is reached. Type of fluid used is at the discretion of the treating clinician(s). The rate may be adjusted, based upon individual patient requirements, at the discretion of the treating clinician(s). Additionally, if the treating clinician(s) discerns a risk to patient safety, a lower CVP may be used.

Blood pressure management

An arterial line is recommended for continuous blood pressure monitoring. If either mean arterial pressure (MAP) is less than 65 mmHg or systolic blood pressure (SBP) is less than 90 mmHg, after fluid resuscitation to a minimum CVP of 8 mmHg, vasopressors are administered and titrated to a minimum MAP of 65 mmHg or a minimum SBP of 90 mmHg. All sites are expected to use such therapies based on best current evidence. Thus, treating clinician(s) may administer their vasopressor of choice, deemed most appropriate based upon the current evidence, patient requirement and local practice.

If MAP is greater than 90 mmHg, afterload reduction can be initiated to lower MAP to within 65-90 mmHg. The vasodilator agent used is at the discretion of the treating clinician(s). If the treating clinician(s) determines a MAP in excess of 90 mmHg is required, due to patient safety concerns such as a known baseline SBP or MAP in excess of the protocol goals, then the patient should be treated accordingly and recorded on the relevant CRF.

ScvO₂ management

Once the CVP is a minimum of 8 mmHg and either the MAP is a minimum of 65 mmHg or SBP is a minimum of 90 mmHg, the third goal is a minimum $ScvO_2$ of 70%.

[figure not shown]
If the $ScvO_2$ is less than 70% and the post-fluid resuscitation haemoglobin is less than 10g dl⁻¹, then packed red blood cells are transfused. Once the haemoglobin is 10g dl⁻¹ and, if the $ScvO_2$ is still less than 70%, then inotropic support is initiated with dobutamine. Dobutamine dosing is 2.5 ug kg⁻¹ min⁻¹, over thirty minutes initially, then increased by 2.5 ug kg⁻¹ min⁻¹ every thirty minutes until the $ScvO_2$ is 70% or greater. Dobutamine should be reduced/discontinued, at the discretion of the treating clinician(s), if there is concern about a likely, drug-induced tachycardia, arrhythmia, or if a maximum dose of 20 ug kg⁻¹ min⁻¹ is attained.

If the ScvO₂ remains low, then the patient may be intubated, sedated and paralysed, if not done previously to decrease oxygen consumption.

Post-goal monitoring

Once all goals are met, the patient is monitored continuously for the remainder of the intervention period (a total of six hours). If an end-point subsequently falls below its goal, then the early, goal-directed, resuscitation protocol re-cycles. At the end of six hours, the patient returns to standard care and continuous $ScvO_2$ monitoring is no longer mandated.

Figure 2. ProMISe early, goal-directed, resuscitation protocol

